10.4.2 General guidelines for reporting adverse events

- All AEs, regardless of seriousness or relationship to IMP, spanning from the signature of the informed consent form until the end of the study as defined by the protocol for that patient, are to be recorded on the corresponding page(s) or screen(s) of the e-CRF.

Whenever possible, diagnosis or single syndrome should be reported instead of symptoms. The Investigator should specify the date of onset, intensity, action taken with respect to IMP, corrective treatment/therapy given, additional investigations performed, outcome, and his/her opinion as to whether there is a reasonable possibility that the AE was caused by the IMP or by the study procedure(s). The causal relationship will be assessed either to FQ or OZ439 which are considered as distinct entities.

- The Investigator should take appropriate measures to follow all AEs until clinical recovery is complete and laboratory results have returned to normal, or until progression has been stabilized, or until death, in order to ensure the safety of the patients. This may imply that observations will continue beyond the last planned visit per protocol, and that additional investigations may be requested by the monitoring team up to as noticed by the Sponsor.
- When treatment is prematurely discontinued, the patient's observations will continue until the end of the study as defined by the protocol for that patient.
- Laboratory, vital signs or ECG abnormalities are to be recorded as AEs only if:
 - Symptomatic and/or
 - Requiring either corrective treatment or consultation, and/or
 - Leading to IMP discontinuation or modification of dosing, and/or
 - Fulfilling a seriousness criterion, and/or
 - Defined as an AESI

10.4.3 Instructions for reporting serious adverse events

In the case of occurrence of an SAE, the Investigator must immediately:

- ENTER (within 24 hours) the information related to the SAE in the appropriate screens of the e-CRF; the system will automatically send a notification to the monitoring team after approval of the Investigator within the e-CRF or after a standard delay.
- SEND (preferably by fax or e-mail) a photocopy of all examinations carried out and the dates on which these examinations were performed, to the representative of the monitoring team whose name, fax number, and email address appear on the clinical trial protocol. Care should be taken to ensure that the patient's identity is protected and the patient's identifiers in the clinical trial are properly mentioned on any copy of a source document provided to the Sponsor. For laboratory results, include the laboratory normal ranges.
- All further data updates should be recorded in the e-CRF as appropriate, and further documentation as well as additional information (for laboratory data, concomitant medications, patient status, etc) should be sent (by fax or e-mail) to the monitoring team within 24 hours of knowledge of the SAE. In addition, every effort should be made to further document any SAE that is fatal or life threatening within a week (7 days) of the initial notification.
- A back-up plan (using a paper CRF process) is available and should be used when the e-CRF system does not work.

Any SAE brought to the attention of the Investigator at any time after the end of the study for the patient and considered by him/her to be caused by the IMP with a reasonable possibility, should be reported to the monitoring team.

10.4.4 Guidelines for reporting adverse events of special interest

For AESIs, the Sponsor must be informed immediately (ie, within 24 hours), as per SAE notification guidelines described in [Section 10.4.3](#), even if not fulfilling a seriousness criterion, using the corresponding screens in the e-CRF. Instructions for AE reporting are summarized in [Table 10](#).

10.4.5 Guidelines for management of specific laboratory abnormalities

Decision trees for the management of certain laboratory abnormalities by Sanofi are provided in [Appendix D](#).

The following laboratory abnormalities should be monitored, documented, and managed according to the related flow chart in protocol appendices.

- Neutropenia
- Thrombocytopenia
- Increase in ALT
- Acute renal failure
- Suspicion of rhabdomyolysis

NOTE: Increase in ALT is considered as AESI (see [Section 10.4.1.4](#))

Table 10 - Summary of adverse event reporting instructions

Event category	Reporting timeframe	Specific events in this category	Case Report Form completion		
			AE form	Safety Complementary Form	Other specific forms
Adverse Event (non-SAE, non-AESI)	Routine	Any AE that is not SAE or AESI	Yes	No	No
Serious Adverse Event (non-AESI or AESI)	Expedited (within 24 hours)	Any AE meeting seriousness criterion per Section 10.4.1.2	Yes	Yes	No
Adverse Event of Special Interest	Expedited (within 24 hours)	Pregnancy	Yes	Yes	Yes
		Symptomatic overdose	Yes	Yes	No
		ALT \geq 3 ULN (if baseline ALT<ULN) and ALT \geq 2 x baseline (if baseline ALT \geq ULN)	Yes	Yes	Yes
		QTcF \geq 500 ms or Δ QTcF >60 ms from baseline	Yes	Yes	No

SAE: Serious AE, AESI: AE of special interest, ALT: alanine transferase, ULN: upper limit of normal, QTcF: QT interval corrected with Fridericia method, ms: millisecond

10.5 OBLIGATIONS OF THE SPONSOR

During the course of the study, the Sponsor will report in an expedited manner:

- All SAEs that are both unexpected and at least reasonably related to the IMP (Suspected unexpected serious adverse reaction [SUSAR]), to the regulatory authorities, IECs/IRBs as appropriate and to the Investigators.
- All SAEs that are expected and at least reasonably related to the IMPs to the regulatory authorities, according to local regulations.

Any other AE not listed as an expected event in the Investigator's Brochure or in this protocol will be considered unexpected.

In case of a SUSAR, Sanofi Global Pharmacovigilance and Epidemiology will utilize XGRID to reveal medication assignment for regulatory reporting requirements for the particular case.

The Sponsor will report in the clinical study report all safety observations made during the conduct of the trial.

10.6 SAFETY INSTRUCTIONS

10.6.1 Development of complicated malaria

The development of symptoms suggestive of severe (also defined as complicated) malaria will be investigated throughout the study. Severe malaria is considered in case of clinical features and/or laboratory and other findings as defined in [Appendix A](#).

Any symptom suggestive of severe malaria will be considered life-threatening and reported as unexpected SAE.

The patient will be treated according the local recommendations for severe malaria.

10.6.2 PK sampling in case of QTcF \geq 500 ms or QTcF prolongation $>$ 60 ms and/or ALT \geq 3xULN

Patients having experienced a QTcF \geq 500 ms or QTcF prolongation $>$ 60 ms from baseline and/or with ALT \geq 3 ULN will be measured for circulating levels for OZ439, FQ and SSR97213 immediately after a QTcF \geq 500 ms and/or ALT \geq 3xULN is reported to the investigator.

11 STATISTICAL CONSIDERATIONS

The material of Section 11 of the Clinical Trial Protocol is the basis for the Statistical Analysis Plan for the study. This plan may be revised during the study to accommodate Clinical Trial Protocol amendments and to make changes to adapt to unexpected issues in study execution and data that affect planned analyses. These revisions will be based on blinded review of the study and data, and a final plan will be issued at the latest 6 to 8 weeks before final database lock.

11.1 DETERMINATION OF SAMPLE SIZE

This protocol is adaptive allowing futility at pre-specified interim points during the conduct of the study. At each interim time point, tests for futility will be performed. Recruitment will cease to a particular treatment arm if the pre-specified criterion for futility is reached. Interim assessment of futility will occur after recruitment of approximately 50 evaluable patients per treatment arm for the 1st futility analysis and every 25 evaluable patients per treatment arm thereafter for the 3 other interim analyses (including 75, 100 and 125 evaluable patients per treatment arm, respectively). Recruitment continues until each treatment arm is deemed to be futile or until 150 evaluable patients per treatment arm for the final analysis is reached. In case of high recruitment rate (ie, fast recruitment), not all the futility analyses may be performed.

Given the adaptive nature of the study design, the total number of patients to be recruited can only be estimated. Simulations for different PCR-adjusted ACPR responses at Day 28 showed that a sample size of 150 evaluable patients per treatment arm will provide $\geq 80\%$ probability to reject the null hypothesis (H_0 : probability of PCR-adjusted ACPR at Day 28 ≤ 0.90) at the final analysis, for the true rate of 96.4%. Recruitment will therefore continue until each treatment arm is deemed to be futile or until 150 evaluable patients per treatment arm is reached.

In addition, a minimum of 15 African patients older than 5 years per treatment arm (likely to have higher NAI and therefore not included in the efficacy analyses) will be included for the DMC safety review.

Lower numbers of patients per treatment arm may be recruited in the event of a poorly efficacious dose or doses (ie, futility).

Thus the targeted number of African patients recruited to this study will be approximately 495 (in case of 3 treatment arms, scenario A, approximately 165 patients/arm) or approximately 662 (in case of 4 treatment arms, scenario B, approximately 165 patients/arm).

11.2 DISPOSITION OF PATIENTS

Screened patients (counts and percentages) defined as any patient who signed the informed consent and met the inclusion criteria, screen failures and reason of screened failures will be provided for all patients and separately for each cohort.

Randomized patients consist of all patients with a treatment kit number allocated and recorded in IVRS/IWRS database at visit 2 (Day 0), and regardless of whether the treatment kit was used or not.

Patients treated without being randomized by IVRS will not be considered as randomized and will not be included in any population.

In the unlikely event of any patient being randomized more than once, only the data associated with the first randomization will be used in any analysis population. The safety experience associated with any later randomization will be assessed separately.

The safety experience of patients treated and not randomized will be reported separately, and these patients will not be in the safety population.

In addition, a summary table (count and percentage) will be provided on the randomized population by treatment arm, country and center. Same summary will be provided also for each cohort (one table per cohort).

Percentages will be calculated using the number of patients randomized as the denominator.

11.3 ANALYSIS POPULATIONS

The analysis populations described below will be summarized by treatment group in a table given numbers and percentages based on randomized population. Same summary tables will be provided by treatment group and by cohort (one table per cohort). Within Cohort 1, data may also be summarized separately for Asian and African patients.

11.3.1 Randomized population

The randomized population is defined as all patients who have given their informed consent and who have been allocated to a randomized treatment regardless of whether the treatment kit was used or not.

11.3.2 Efficacy populations

Two efficacy analysis populations will be considered ie, Modified intent-to-treat (mITT) and Per-protocol (PP) populations focused on the “lower” NAI African population.

For the Asian patients and for the higher NAI population defined as all randomized patients >5 years in Africa (Cohort 1 & 2), with parasitologically confirmed malaria at baseline, who received at least the single administration OZ439/FQ, separate statistical reporting on all efficacy endpoints will be provided as secondary analyses.

The primary efficacy analysis population will be the per-protocol (PP) population defined as African patients of lower NAI; children ≤5 years in Africa (see [Section 11.3.2.2](#)).

11.3.2.1 Modified intent-to-treat population

Modified intent-to-treat (mITT) population is defined as all randomized African patients of “lower” NAI population (ie defined as children ≤ 5 years in Africa) with parasitologically confirmed malaria at baseline, who received at least the single administration OZ439/FQ, ie, who did not need rescue therapy due to vomiting during IMP administration (see [Section 8.9](#)).

African patients with age >5 years old, and Asian patients will not belong to the mITT.

Patients in the mITT population will be analyzed according to the treatment arm allocated by randomization.

11.3.2.2 Per-protocol (PP) population

Per-protocol (PP) population is defined as mITT patients who do not qualify for a major deviation, as defined in the statistical analysis plan.

11.3.3 Safety population

The Safety population considered for safety analyses will be the randomized population including lower and higher NAI population who did actually receive at least one dose or part of a dose of the single administration OZ439 800 mg & FQ. Patients will be analyzed according to the treatment actually received (OZ439/FQ).

In addition, randomized patients for whom it is unclear whether they took the study medication will be included in the safety population as randomized.

11.3.4 Pharmacokinetic population

The PK analysis will be performed on all treated patients (safety population) with at least one evaluable blood sample for PK post double-blind IMP administration and with adequate documentation of date of dosing and date of sampling.

11.3.5 Pharmacokinetic/pharmacodynamic population

PK/PD analyses using PCR-adjusted ACPR efficacy endpoint will be performed on all patients included in both the pharmacokinetic and the Per-Protocol (PP) populations.

All patients included in the pharmacokinetic population and having at least one post-baseline assessment in QTc evaluation regarding the three PK/QTc analyses (one for Cohort 1a a second polling Cohorts 1a & 1b and final analysis including all cohorts) will be the pharmacokinetic/pharmacodynamic population.

11.4 STATISTICAL METHODS

11.4.1 Demographics and baseline characteristics

Continuous variables (age, weight) and qualitative variables (gender, race and BMI [<30 or ≥ 30 kg/m²]) will be summarized in descriptive statistics by treatment arm and for all patients, and separately for each cohort (one table per cohort) for the randomized population. Within Cohort 1, demographics and baseline characteristics will also be summarized separately for Asian and African patients.

Other baseline characteristics like general medical history, previous medications defined as those started before the first intake of study drug and concomitant medications defined as those taken concomitantly to the study drug will be summarized by treatment arm and for all patients, and separately for each cohort (one table per cohort) for the randomized population:

- Summary of all medical history (number and percentage of patients) by primary system organ class (SOC) and high Level Term (HLT).
- Summary of Prior medications taken prior to first IMP intake (number and percentage of patients) by anatomic class and therapeutic class.
- Summary of concomitant medications (number and percentage of patients) by anatomic class and therapeutic class.

11.4.2 Extent of study treatment exposure and compliance

The listing of patients receiving IMP from specified batch will also be provided by cohort, treatment arm and patient. Besides, a listing sorted by site and cohort will be provided to display the randomization scheme (block number, sequence order with block, treatment arm, date and time of treatment allocation) of the study.

11.4.2.1 Extent of investigational medicinal product exposure

Since this is a single dose administration, duration of IMP exposure will not be calculated.

11.4.2.2 Compliance

A given administration will be considered noncompliant if the patient did not take the planned dose of treatment as required by the protocol. No imputation will be made for patients with missing or incomplete data. Since this is a single dose administration, treatment compliance, above-planned and under-planned dosing percentages will not be calculated.

11.4.3 Analyses of efficacy endpoints

The primary final analysis will be carried out on the per-protocol (PP) population. Major protocol deviations disqualifying patients for the PP population will be described in the statistical analysis plan.

All statistical analyses on secondary efficacy endpoints will be done on the PP population. However, in case mITT and PP populations differ by more than 5%, statistical analysis of the primary endpoint ACPR at Day 28 will be carried out on the mITT population.

A separate reporting on primary and secondary efficacy endpoints will be provided on “higher” NAI population; (Africans >5 years), and Asian population.

11.4.3.1 Analysis of primary efficacy endpoint

See [Section 9.1.1](#) for primary efficacy endpoint details.

- PCR-adjusted ACPR (4-term composite criterion) at Day 28.

Within each treatment arm, the following null hypothesis will be tested:

$$H_0: p \leq 0.90$$

Against the one sided alternative:

$$H_1: p > 0.90 \text{ where } p \text{ is the probability of PCR-adjusted ACPR at Day 28.}$$

The study will follow a group sequential design with up to 4 interim futility analyses, the first one when approximately 50 patients per treatment arm have reached Day 28 and thereafter every time another 25 patients per treatment arm (until the final analysis including 150 patients) have reached Day 28.

At each interim analysis, based on PP population one of the following potential decisions is to be made:

- The treatment arm is stopped for futility if the posterior probability of H_0 (that is, response rate is below 90%) given the data accumulated at the look for the treatment arm in question is too large, that is, $\Pr(H_0|\text{data}) \geq 0.30$.
- The treatment arm advances to the next stage if the above conditions is not met (even if the observed response rate is 95% or greater).

A Beta (9.5, 0.5) distribution will be used as prior distribution for the response rate and combined with a binomial likelihood to get a Beta posterior distribution (9.5 + x, 0.5 + N-x) with x is the number of successes out of N patients and calculate the posterior probability.

At the final analysis, providing the treatment arm has not been stopped for futility, the null hypothesis will be rejected and binary endpoints such PCR-adjusted ACPR, ETF, LCF and LPF at Day 28 will be analyzed thanks to a frequency table ie, proportion, percentage and exact binomial 95% confidence intervals (two-sided by using Clopper-Pearson method for calculating binomial confidence intervals) on the per-protocol (PP) population by cohort and treatment arm (one table including all patients and one table per cohort). Efficacy of the treatment arm demonstrated if the lower limit of the exact 95% confidence interval of PCR-adjusted ACPR rate is >90%.

Same frequency table will be provided by treatment arm for children population (ie, including only Cohort 3 & 4).

11.4.3.2 Analyses of secondary efficacy endpoints

See [Section 9.2.1](#) for secondary efficacy endpoints details

- PCR-adjusted ACPR (4-term composite criterion) at Day 42 and Day 63
PCR-adjusted ACPR, Early Treatment Failure (ETF), Late Clinical Failure (LCF) and Late Parasitological Failure (LPF) will be analyzed at Day 42 and Day 63 separately thanks to a frequency table ie, proportion, percentage and exact binomial 95% confidence intervals (two-sided by using Clopper-Pearson method for calculating binomial confidence intervals) by cohort and treatment arm (one table including all patients and one table per cohort).
- PCR-crude ACPR at Days 28, 42 and 63
Same analysis using Clopper-Pearson method will be done on PCR-crude ACPR at Days 28, 42 and 63. The dose-response association of single-dose OZ439/FQ for PCR-crude ACPR will also be evaluated.
- Time to re-emergence, to recrudescence, to re-infection, time to parasite clearance (PCT) and time to fever clearance (FCT).
Time to event variables (like time to re-emergence, time to recrudescence, time to re-infection, [FCT], [PCT]) will be analyzed using Kaplan-Meier estimators. Unless specified otherwise, all survival times will be calculated from the date/hour of first study drug intake to the first time to which the event occurred. For each variable, an overall overview including number of events (frequency and %), 25%, median and 75% quantile with 95% CI (expressed in weeks), cumulative incidence of events with 95% CI will be provided in a summary table for all patients and for each cohort separately. Survival curves will be plotted by representing each treatment arm for all patients and separately for each cohort.
- Parasite reduction ratio (PRR)
The calculations and modeling for the PRR will be further discussed in the SAP. This will be calculated using microscopic and, when available, qPCR determined parasitemia.
- Parasitemia
Descriptive statistics (n, mean, geometric mean, standard deviation, median, Q1, Q3, minimum, and maximum) for parasitemia data (number of parasites/ μ L) (raw data and absolute change from baseline) will be displayed at each post-baseline assessment. Time profile plots (Mean \pm SEM) of parasitemia will be provided for each treatment arm, one curve per arm and also for each cohort separately. These analyses will be done using microscopic and qPCR (in patients >5 years) determined parasitemia.

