3 LIST OF ABBREVIATIONS

° C:	degrees Celsius
ACPR:	adequate clinical and parasitological response
ACT:	artemisinin-based combined therapy
AESI:	adverse event of special interest
AS:	artesunate
BP:	blood pressure
CRF:	case report form
DBS:	dry blood sample
DMC:	data monitoring committee
DPS:	dry plasma sample
DRF:	discrepancies resolution form
e-CRF:	electronic case report form
ETF:	early treatment failure
FCT:	fever clearance time
FQ:	ferroquine
GCP:	good clinical practices
HR:	heart rate
IA:	interim analysis
ICH:	International Conference of Harmonization
IMP:	investigational medicinal product
IRB/IEC:	institutional review board/independent ethics committee
LCF:	late clinical failure
LFT:	liver function test
LOQ:	limit of quantification
LPF:	late parasitological failure
MMV:	Medicines for Malaria Venture
MPC:	minimum parasitocidal concentration
ms:	millisecond
NAI:	naturally acquired immunity
OZ439:	artefenomel
P. falciparum :	Plasmodium falciparum
PCR:	polymerase chain reaction
PCT:	parasite clearance time
PK:	pharmacokinetic
PRR:	parasite reduction rate
RDT:	rapid diagnostic test
SAE:	serious adverse event
SUSAR:	suspected unexpected serious adverse reaction
TEAE:	treatment emergent adverse event
TPGS:	alpha tocopherol polyethylene glycol 1000 succinate
WHO:	World Health Organization

GLOSSARY OF TERMS

qPCR (quantitative polymerase chain reaction)

A polymerase chain reaction procedure is used to quantify the amount of *Plasmodium falciparum* (*P. falciparum*)-specific DNA present and is transformed into number of parasites/ μ L.

RT-PCR (reverse transcriptase polymerase chain reaction)

Gametocytes are differentiated from asexual forms by targeting RNA transcripts of gametocyte-specifically expressed genes (Pfs25).

Recrudescence

Recrudescence is defined as the appearance of asexual parasites after clearance of initial infection with a genotype identical to that of parasites present at baseline. Recrudescence must be confirmed by microscopy (positive blood smear) and polymerase chain reaction (PCR) analysis.

Re-infection

Re-infection is defined as the appearance of asexual parasites after clearance of initial infection with a genotype that differs from that of parasites present at baseline. Re-infection must be confirmed by microscopy (positive blood smear) and PCR analysis. Confirmed new infection will not be regarded as treatment failure or recrudescence.

Re-emergence/Recurrence

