Re-emergence (recrudescence and re-infection) is defined as the appearance of asexual parasites after clearance of initial infection irrespective of genotype.

PCR crude

PCR-crude adequate clinical and parasitological response (ACPR) does not distinguish between re-infection (by a new clone of parasite) and recrudescence (re-emergence of the original clone of parasite that is present at baseline).

PCR-adjusted

PCR-adjusted ACPR applies only to recrudescence (re-emergence of the original clone of parasite that is present at baseline). Recrudescence is distinguished from re-infection by genotyping the parasite clone.

SSR97213

N-demethyl derivative, active metabolite of ferroquine (FQ)

CLASSIFICATION OF TREATMENT OUTCOMES (ADAPTED FROM WHO, 2009) (1)

Parasitemia will be evaluated locally with blood smear.

Early treatment failure (one the following)

- Danger signs or severe malaria on Day 1, 2 or 3 in the presence of parasitemia;
- Parasite count on Day 2 higher than on Day 0, irrespective of axillary temperature;
- Parasitemia on Day 3 with axillary temperature $\geq 37.5^{\circ}\text{C}$;
- Parasite count on Day 3 $\geq 25\%$ on Day 0.

Late clinical failure

- Danger signs or severe malaria on any day between Day 4 and Day 63 in the presence of parasitemia, without previously meeting any of the criteria of early treatment failure;
- Presence of parasitemia and axillary temperature ≥ 37.5 degrees Celsius ($^{\circ}\text{C}$) (or history of fever) on any day between Day 4 and Day 63, without previously meeting any of the criteria of early treatment failure.

Late parasitological failure

- Presence of parasitemia on any day between Day 7 and Day 63 and axillary temperature $< 37.5^{\circ}\text{C}$, without previously meeting any of the criteria of early treatment failure or late clinical failure.

Adequate clinical and parasitological response (ACPR)

- Absence of parasitemia on Day 28 (or Day 42 or Day 63), irrespective of axillary temperature, without previously meeting any of the criteria of early treatment failure or late clinical failure or late parasitological failure.

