4.2.2 Dose Rationale

Doses for DRI12805 were selected based on clinical data obtained in Human Challenge Model studies for OZ439, Phase IIa data for OZ439 (MMV_OZ439_10_002), Phase IIb FQ/AS (DRI10382 results) and predicted QTc prolongation for FQ as discussed below.

Based on modeling and simulation of the parasite clearance kinetics of OZ439, the MPC (minimum parasitocidal concentration) for OZ439 was estimated to be 3-6 ng/mL. Time above MPC for 800 mg OZ was estimated to be approximately 200 h.

This was confirmed in a Phase IIa study of the acute efficacy (up to 36 hours post-dose) of OZ439 against *P. falciparum* and *P. vivax* malaria in a PoC study in Asian adult patients (MMV_OZ439_10_002) leading to a 97.9% reduction in parasite concentration by 36 hours for *P. falciparum* for all doses investigated (200 to 1200 mg).

Assuming an 11-fold reduction in log₁₀ parasitemia is sufficient for effective therapy of patients (malaria patient parasitemia is between 10¹¹ and 10¹² parasites) PK/PD modeling suggests that a single dose of OZ439 at 800 mg can be considered as effective therapy when administered alone with around 11-fold decrease in log₁₀ parasitemia.

In DRI10382, PCR-adjusted Day 28 cure rate was 93.3, 97.1 and 96.8% after 100, 200 & 300 mg (2, 4 & 6 mg/kg) of FQ respectively when given in combination with AS over 3 days in children. A dose effect was observed for secondary criteria (uncorrected Day 28 cure rate) with values of 50.0%, 60.0% and 74.2% after 2, 4 and 6 mg/kg x 3 days respectively, in pediatric population (8, 9).

After simulations using POP PK model in children and 55 kg adults, FQ and SSR97213 Day 28 concentrations obtained after 600 mg single dose (or equivalent dose in children, see Table 2) are similar as compared to Day 28 concentration obtained in children after 4 mg/kg x 3 days (corresponding to 200 mg x 3 days). Thus assuming that OZ439 800 mg single dose performs at least as well as AS 200 mg x 3 days (internal MMV data show that OZ439 800 single dose performs better than 150 mg x 3 days di-hydro artemisinin) efficacy expected after 600 mg FQ /800 mg OZ (expressed in adult dose) single dose should be similar in children and in 55 kg adults to efficacy after 200 mg FQ/ 200 AS x 3 days (expressed in adult dose) with PCR-adjusted Day 28 cure rate of 97% in pediatrics.

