5.2 SECONDARY OBJECTIVES

To evaluate the efficacy of OZ439/FQ:

- To determine the incidence of recrudescence and re-infection.
- To determine the time to relief of fever and parasite clearance.

To evaluate the safety and tolerability of OZ439/FQ in adults and children.

To evaluate the pharmacokinetics of OZ439/FQ:

- To characterize the pharmacokinetics of OZ439 in plasma, FQ and its active metabolite SSR97213 in blood.
- To determine the blood/plasma ratio for FQ and SSR97213 in some patients at limited time points in selected sites.

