8.9 RESCUE TREATMENT FOR MALARIA

The use of a rescue therapy is recommended in the following cases:

- Vomiting during or after FQ dosing or vomiting within 35 minutes after OZ439 re-dosing
- Treatment failure as-per protocol section “Classification of Treatment Outcomes”

The use of established anti-malarial drug combination per WHO recommendations (1) or local guidelines is to be considered as a rescue therapy and the choice of the best therapeutic option is left at Investigator’s decision.

In case of rescue therapy is given, where possible, a PK (OZ439 and FQ) sample should be taken before giving rescue therapy.

Before giving established ACT:

- Blood films and parasite genotyping must be taken for all patients.
- RT-PCR and qPCR for patients >5 years only.

Following administration of established ACT, patients should be managed according to local standard of care practices. Safety data should continue to be collected in the e-CRF, according to the study schedule, and up to the end of the study even if re-emergence is confirmed.

Patients who will have received a rescue treatment after the OZ439/FQ has failed will be part of the Per-Protocol Population (see [Section 11.3.2.2](#)) whereas patients who will have received a rescue treatment because of vomiting during IMP administration will be part of the safety analyses only.

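### Cumulative incidence of recrudescence and of re-infection is tabulated from Kaplan-Meier, which with the usual censoring gives a net risk that generally exceeds the actual incidence

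*Protocol*

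**What the plan says.** One secondary objective in Protocol Section 5.2 is "To determine the incidence of recrudescence and re-infection". Section 11.4.3.2 serves it with time-to-event variables that "will be analyzed using Kaplan-Meier estimators": re-emergence, recrudescence, re-infection, and parasite and fever clearance. For each variable the summary is to give "number of events (frequency and" percentage), quartiles, and "cumulative incidence of events with 95% CI will be provided in a summary table for all patients" and by cohort. No competing-risk estimator is named. No rule says what happens to a patient in the recrudescence analysis who has a re-infection first, or the reverse.

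Four other places bear on whether the two events compete:

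- The treatment outcome classification at the end of Section 3 starts its definition of late parasitological failure with "Presence of parasitemia on any day between Day 7 and Day 63 and axillary temperature" below 37.5°C. It sets no genotype condition.
- Section 8.9 says "The use of a rescue therapy is recommended in the following cases", and treatment failure under that classification is one of the cases.
- Sections 10.1.4 to 10.1.6 tie genotype sampling to the first recurrence after initial clearance. Table 1, footnote f, sends the tests to a central laboratory, on spots collected earlier.
- The glossary in Section 3 states "Confirmed new infection will not be regarded as treatment failure or recrudescence".

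**The concern.** A patient whose parasites reappear will usually be rescued before the genotype is known, because the film is read locally and the genotype comes later from a central laboratory. After that the other type of recurrence can hardly be observed. Recrudescence and re-infection therefore behave as competing events.

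One minus Kaplan-Meier, with the other event censored, answers a hypothetical question: what share would recrudesce if re-infection could not happen? That is a legitimate drug-effect measure, but it is not the incidence in the objective or in the table label.

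Section 4.2.2 expects the trial to document what FQ adds to long-term prevention of both events and to support a Phase 3 dose choice. If re-infection rates differ by dose, the distortion differs by arm and falls on that comparison.

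**Working it through.** **The plan's own figures.** The protocol gives no expected incidence for either event, so there is none to reproduce. Its sample-size claim (at least 80% power with 150 per arm at a true rate of 96.4%) does reproduce: 82.5% without and 81.7% with the four futility looks. This point does not touch it.

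**Direction.** Let h1 and h2 be the cause-specific hazards of recrudescence and re-infection, and S1 and S2 the matching exponentials of minus the cumulative hazard.

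- Actual incidence: CIF1(t) = ∫ h1·S1·S2.
- Kaplan-Meier with the other event censored: 1−KM1(t) = ∫ h1·S1 = 1−S1.
- The gap grows at rate h1·S1·(1−S2) ≥ 0, so it is never negative and never shrinks over follow-up.
- The two Kaplan-Meier figures together exceed re-emergence, 1−S1·S2, by (1−S1)(1−S2).

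**Inputs for size.** Section 4.2.2 quotes the earlier paediatric FQ/artesunate study at Day 28. PCR-adjusted cure was 93.3, 97.1 and 96.8%. Uncorrected cure came "with values of 50.0%, 60.0% and 74.2% after 2, 4 and 6 mg/kg x 3 days respectively". Assuming a common denominator, recrudescence is 6.7, 2.9 and 3.2%, and re-infection is the remaining 43.3, 37.1 and 22.6%.

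**Constant hazards to Day 63 (assumption).** S(63) = S(28)^(63/28) = S(28)^2.25. With s the share of recurrences that are recrudescence, CIF = s(1−S) and 1−KM = 1−S^s.

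- Low: s = 0.067/0.500 = 0.134 and S = 0.500^2.25 = 0.210. CIF = 0.134 × 0.790 = 10.6%; 1−KM = 1−0.210^0.134 = 18.9%.
- Middle: s = 0.029/0.400 and S = 0.600^2.25 = 0.317. CIF = 5.0%; 1−KM = 8.0%.
- High: s = 0.032/0.258 and S = 0.742^2.25 = 0.511. CIF = 6.1%; 1−KM = 8.0%.

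Re-infection at Day 63, CIF against 1−KM: 68.4 and 74.1% (low), 63.4 and 65.6% (middle), 42.8 and 44.5% (high).

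In the low-dose arm the two Kaplan-Meier figures add to 93.0%, against re-emergence of 79.0%. The excess is 0.189 × 0.741 = 14.0 points. The two CIFs add to 79.0%.

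**Sensitivity: recrudescence at Day 63, CIF against 1−KM (%)**

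| Assumption | Low | Middle | High |
|---|---|---|---|
| Recrudescence stops at Day 28 | 6.7 / 8.9 | 2.9 / 3.6 | 3.2 / 3.6 |
| Recrudescence stops at Day 42 | 8.7 / 13.0 | 3.9 / 5.4 | 4.5 / 5.4 |
| Constant hazards | 10.6 / 18.9 | 5.0 / 8.0 | 6.1 / 8.0 |

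The low-dose overstatement is 2.2, 4.3 or 8.3 points, and the high-dose overstatement 0.4, 0.9 or 1.9. A further run, with recrudescence from Day 7 to 42 and re-infection only from Day 14, gives 4.3 (low) and 1.0 (high).

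Across these runs re-infection at Day 63 is overstated by 4.4 to 7.2 points (low) and 1.2 to 2.4 (high).

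If all recrudescences came before any re-infection, the recrudescence figure would be unbiased. Only re-infection would be overstated; at Day 28, low dose, 0.433/0.933 = 46.4% against 43.3%.

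**Dose contrasts.**

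- Low minus high under constant hazards: 18.9−8.0 = 10.9 points by Kaplan-Meier, 10.6−6.1 = 4.5 by CIF. If recrudescence stops at Day 28, about 5.2 against 3.5.
- Middle and high: Kaplan-Meier shows 8.0 and 8.0%, no contrast, where the CIFs are 5.0 and 6.1%.

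**The case against.** The strongest reply is that the bias depends on a rule that the protocol does not write. Censoring conventions are commonly left to the analysis plan, and keeping patients with the other event in the risk set to Day 63 would remove the overstatement. This stands as a condition. But the protocol does fix the estimator and the label, and the usual reading of Kaplan-Meier censors at the other event.

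The incidence objective is also partly served elsewhere. The raw event percentages in the same summary, and the PCR-adjusted and crude ACPR tables at Days 28, 42 and 63, are not inflated in this way. That limits the harm, but the same table would still carry a mislabelled column.

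Net risk is also defensible for comparing doses, since the glossary does not count a confirmed new infection as failure. That is a reason to keep the curves, not to call them incidence.

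Three stronger readings are tempting and not supported:

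- A reader might infer that Kaplan-Meier generally exaggerates the dose effect. The middle-high pair shows the opposite.
- A reader might take the 8-point figure as the expected error. It is the largest of the scenarios, and rests on Day 28 rates extrapolated to Day 63 from FQ given for three days with artesunate. Those are not this trial's arms, so a largest error in this trial's lowest-dose arm is a projection.
- A reader might infer that a first recurrence strictly removes the patient from risk. Rescue is recommended, not mandatory, and Section 10.1.6 still schedules films and blood spots for all patients.

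**Conclusion.** The point holds as a minor one about estimator and label. With the usual censoring at the other event, the tabulated figures for recrudescence and re-infection are net risks that generally exceed the incidence the objective names. The direction follows from the algebra.

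The size is illustrative only: about 2 to 8 points for low-dose recrudescence at Day 63, 0.4 to 1.9 at the highest dose, and zero for recrudescence if it always came first. It rests on borrowed rates, assumed hazard shapes and near-complete ending of observation at first recurrence. Where re-infection differs between arms, the distortion differs too, and it can widen or narrow a dose contrast.

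These are descriptive secondary endpoints. The primary ACPR test and time to re-emergence do not change.

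**What to change.** In Section 11.4.3.2, compute the tabulated cumulative incidence of recrudescence and of re-infection, with 95% CI, by the Aalen-Johansen estimator, treating the other event as competing. Keep the Kaplan-Meier curves for these two variables, label them as net risk, and state that patients are censored at the other event. Leave time to re-emergence on Kaplan-Meier.

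This needs no new data and no design change, only one software option and one extra table column. The downside is that the report must explain two estimates for each event.
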